**Introduction:**

Monitoring of fetal heart rate and uterine contractions are crucial to determining fetal well-being and labor progress. The current methods available for monitoring fetal heart rate and contraction frequency and intensity are either externally applied (i.e. Doppler ultrasound for determining the fetal heart rate and tocodynamometry for measuring contractions) or require invasive insertion in the presence of cervical dilation and rupture of membranes (i.e. fetal scalp electrode for determining fetal heart rate and intrauterine pressure catheter for measuring contractions). While the invasive devices represent the

Version 5.13; June 19, 2020

“gold standard” for monitoring, their invasive nature comes with limitations of when they can be used and has risks of infection, etc.i

The noninvasive devices have limitations in their accuracy. Although the tocodynamometer is noninvasive, it can only be used to measure contraction frequency. Additionally, it is difficult to obtain an accurate tracing in patients that are obese or in pain and unable to lie still. The fetal Doppler averages the last three beats, which limits its accuracy. Both are limited in that maintaining proper placement on the maternal abdomen is limited in the presence of both maternal and fetal movement.

Obesity during pregnancy presents significant challenges to monitoring uterine activity and fetal heart rates with the usual external devices. The tocodynamometer works by through a button on the underside of the device that is pressed when the uterus becomes firm and moves anteriorly in the maternal abdomen during a contraction. The ability of the uterus to “push” this button becomes more limited the greater the amount of adipose tissue interposed between it and the button. Additionally, with obesity keeping the tocodynamometer and the Doppler ultrasound device (used to monitor the fetal heart rate noninvasively) in their proper positions in order to obtain useable tracing becomes a significant obstacle.

For these reasons developing a device that is noninvasive but has similar accuracy to a fetal scalp electrode and an intrauterine pressure catheter is of paramount importance.

Obstetrical triage visits are most often secondary to uterine contractions either at term or pretermii. It is however challenging to determine whether a patient is in active labor and in need of admissioniii. The predictive value of current objective and non-objective methodologies of term or preterm deliveries remain poor. The ability to determine true labor from contractions that do not lead to cervical change becomes important in a busy triage, such as those at Montefiore, and is especially important in preterm gestations when interventions such as betamethasone injections, magnesium sulfate for

Version 5.13; June 19, 2020

neuroprotection and tocolysis can lead to decrease fetal morbidity. Women who are not in labor are at risk of medical interventions (e.g. oxytocin and cesarean birth) that can lead to increased risk of morbidity and mortality for mothers and babiesiv, v, vi, vii.

The EUM300 (electrical uterine myography)(OB Tools, Israel) is an FDA approved monitor intended for the evaluation of electrical signals originating in the uterus, thus providing a tool for measuring uterine activity as well as fetal heart rate. It is an external, non-invasive device that uses electrodes placed on the abdomen. The electrical traces can be displayed on screen in real time and data are stored and can be retrieved for later analysis.

The EUM300 was tested and found to be reliable as a non-invasive method for evaluating contractions. It is safe and effective in monitoring uterine contractionsError! Bookmark not defined.,viii. It is able to quantify uterine electrical activity and therefore to measure the strength of uterine contractions noninvasively. Thus, it has the potential to differentiate productive v. nonproductive contractions (as determined by cervical change). Although, there are yet no published studies using the EUM to assess fetal heart rate, fetal heart rate has also been accurately acquired using maternal abdominal sensors associated with this deviceix.

#### Purpose:

We propose to perform a study to validate the accuracy and clinical usefulness of the EUM device by comparing it with simultaneous use of current methods (both external or internal devices) among obese patients and patients with normal body mass indexes (BMI). Our goal is to show that the EUM device is a noninvasive tool of similar utility to the fetal scalp electrode and the IUPC, and superior the traditionally used noninvasive devices (Doppler ultrasound and tocodynamometer).

#### Objectives:

Version 5.13; June 19, 2020

1. Compare the contraction tracings obtained using the EUM device vs. those obtained using the intrauterine pressure catheter vs. those obtained from external tocodynamometer among current obese patients (BMI greater than 30 kg/m^2) and nonobese patients using simultaneously obtained, 30 minute tracings with regards to the frequency of contractions, the duration of contractions, maximum height of the contractions, the total Montevideo units recorded, the timing of the contractions, and the amount of discontinuous tracings from the devices. Of the variables mentioned, the Montevideo units will only be comparable between the IUPC tracings and the EUM device.
2. Compare the fetal heart rate tracing obtained via the EUM device vs. external fetal Doppler vs. fetal scalp electrode (simultaneously obtained, 30 minute tracings will be compared) among obese patients and nonobese patients with regards to the amount of discontinuous/uninterpretable tracing, average fetal heart rate, baseline heart rate, the number accelerations, the number of decelerations, the timing of the accelerations, the timing of decelerations, the maximum fetal heart rate achieved during acceleration, the lowest fetal heart rate achieved during deceleration, and compare the degree of variability in the tracing.
3. Compare tracings of productive vs. non-productive contractions in patients presenting to triage to rule out labor (30 minutes of simultaneously obtained tracings of external tocodynamometer and EUM device will be compared) with regards to the frequency of contractions, the duration of contractions, maximum height of contractions, the timing of the contractions and the amount of discontinuous tracings from both devices, as well as changes in cervical exam on the basis of body mass index. Productive contractions are those that cause a change in cervical exam of 1 cm or more, any change in station or change in effacement of 50% or more.

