- Continuity in readings of fetal heart rate (as measured in the number of minutes without a readable tracing in a 30 minute sample tracing) between EUM and fetal scalp electrode and external fetal heart rate monitoring from the same patient
- Continuity in readings of contractions (as measured in the number of minutes without a readable tracing in a 30 minute sample tracing) between EUM, IUPC and external tocodynamometer from the same patient

Secondary Outcomes:

- Compare average frequency of contractions between the monitoring systems
- Compare duration of contraction between the monitoring systems
- Compare maximum height of the contraction between the monitoring systems
- Compare total Montevideo units obtained between the monitoring systems
- Compare the timing of the contraction between the monitoring systems
- Compare average fetal heart rate between the monitoring systems
- Compare baseline heart rate between the monitoring systems
- Compare the number accelerations between the monitoring systems
- Compare the number of decelerations between the monitoring systems
- Compare the timing of the accelerations between the monitoring systems
- Compare the timing of decelerations between the monitoring systems
- Compare the maximum fetal heart rate achieved during acceleration between the monitoring systems
- Compare the lowest fetal heart rate achieved during deceleration between the monitoring systems
- Compare the degree of variability in the tracing between the monitoring systems. Degree of variability will be defined as the correlation between the tracings. The tracings will be broken down into 4 minute intervals and defined as minimal, moderate or marked variability and compared with each other for accuracy and

Version 5.13; June 19, 2020

consistency. Most accurate will be the internal monitor in each case, i.e. fetal scalp electrode.

- Compare patient satisfaction between the monitoring systems

Inclusion criteria:

- 1) Maternal age >18 years old
- 2) Singleton pregnancy
- 3) Gestational age of 24 completed weeks or greater based on the estimated due date as calculated from last menstrual period or early ultrasound
- 4) Category I (reassuring) fetal heart rate tracing at time of enrollment

Exclusion criteria:

- 1) Fetal anomaly or chromosome defect
- 2) Allergy to silver
- 3) Woman with implanted electronic device of any kind
- 4) Irritated skin or open wound on the abdominal wall

Recruitment Mechanisms:

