#### Device Description:

The EUM300 is composed of three units: Disposable electrode, Maternal unit and Interface unit.

Disposable electrode applied part – Proprietary bio-compatible patch electrode array with nine Ag/AgCl and hydrogel connections. Electrode is made by US based manufacturers: Lead-Lok, Sandpoint, ID and Molex, Naperville, IL.

Maternal Unit – The maternal unit is connected via a proprietary connector to the electrode. The EMG signals are amplified by an analog front-end. OB-Tools Algorithm runs on a DSP board and the result – Fetal Heart Rate and Uterine Activity are transmitted via Bluetooth. The unit contains a 4.2V Li-Ion rechargeable battery. The battery allows 24h of work and must be charged away from the patient.

Interface unit – Wall mount unit translates the information received from a paired Bluetooth Maternal unit. In this setup the EUM is used as a secondary system, one that

Version 5.13; June 19, 2020

is not involved with clinical decisions. In this case a PC computer receives the bluetooth transmission from the maternal unit and saves it into an Excel readable file. A primary monitor that is used for clinical decisions may also be connected to the PC and its data is recorded into the same file for comparison. The file format is a simple 6 column format: Date, Time, EUM UA, EUM FHR, Monitor UA, Monitor FHR. The file can be read and analyzed using Excel, Matlab and other statistical tools.

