Because many of these patients will overlap due to the fact that they will serve as their own control and will be monitored simultaneously for fetal heart rate and change in cervical exam, it is anticipated that the maximum number of patients required in this study will not be more than 220 patients since 55 obese and 55 non-obese patients will be needed and additional patients may be needed to evaluate productive contractions. In addition to comparing the continuity in readings, in assessing contractions, we will also compare average frequency of contractions, the duration of contraction, maximum height of the contraction, the total Montevideo units obtained, the timing of the contraction and the amount of discontinuous tracings from the devices. In assessing fetal heart rate, we will compare average fetal heart rate, baseline heart rate, the number accelerations, the number of decelerations, the timing of the accelerations, the timing of decelerations, the maximum fetal heart rate achieved during acceleration, the lowest fetal heart rate achieved during deceleration, and compare the degree of variability in the tracing. A continuous outcome will be compared using a paired t-test.

Version 5.13; June 19, 2020

As each patient is serving as its own control, missing data is unlikely to be an issue in this study once the patient consents. If the monitoring is less than 30 minutes, these patients will not be used in analysis due to concern for completeness and accuracy.

Safety assessment:

Safety and tolerability will be assessed by recording of adverse events. Adverse events will be reported. Adverse events will be assessed in terms of their seriousness, severity, and relationship to the study device. To date more than 800 patients have used the device in clinical trials and there have been no safety events reported with the use of the device to date.

Potential benefits:

There is no immediate benefit to the subject from her participation in this study. The study results will support the development of the EUM300pro system, which may have clinical importance in providing the care provider with more continuous and accurate monitoring of fetal heart rate and contractions in a less invasive way. These parameters will aid the medical staff in making timely clinical decisions and increasing the chances of attaining a successful treatment and/or delivery.

Potential risks:

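### The paired t-test planned for EUM v. IUPC Montevideo units and contraction height cannot show agreement, and the plan does not state the EUM unit or how EUM Montevideo units are derived

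*Combined protocol and SAP*

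**What the plan says.** Objective 1 lists the contraction variables to be compared across EUM, IUPC and tocodynamometer, among them maximum height and total Montevideo units. It adds that "the Montevideo units will only be comparable between the IUPC tracings and the EUM device".

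The Secondary Outcomes in Materials and Methods include "Compare total Montevideo units obtained between the monitoring systems" and "Compare maximum height of the contraction between the monitoring systems". The Statistics section lists both variables again and then states: "A continuous outcome will be compared using a paired t-test". The only other description of method there is a general reference to routine parametric and nonparametric analysis.

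On what is measured, the Introduction describes the EUM as "intended for the evaluation of electrical signals originating in the uterus". The Device Description says "The EMG signals are amplified by an analog front-end"; an algorithm then produces a uterine-activity channel. That channel is saved beside the fetal monitor's uterine-activity channel, and no unit is given for either. That the IUPC measures pressure follows from its name.

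The Purpose section sets the aim: to validate the accuracy of EUM and to show that it is as useful as the IUPC without being invasive.

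**The concern.** The plan has two gaps at this point.

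1. **Scale.** For Montevideo units or contraction height to be compared as numbers, both devices must report them on a common scale. The plan asserts comparability but gives no unit for the EUM channel, no calibration to pressure and no rule for computing a Montevideo-unit equivalent. The Introduction argues that quantifying electrical activity measures contraction strength. That link is part of what a validation study should test.
2. **Test.** Accuracy against a reference is a question of agreement or, if the scales differ, of tracking. A paired t-test asks only whether the mean difference is zero. The plan contains no limits of agreement, concordance, calibration or equivalence analysis for these two variables. Its one mention of correlation concerns fetal heart rate variability.

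What is at stake is the reading of the study's comparison of contraction strength with the pressure reference. A significant result could be taken as failure of a device that tracks the IUPC closely. A non-significant result could be taken as similarity for a device that does not track it at all.

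**Working it through.** **The plan's own figure.** The only EUM v. IUPC sizing figure concerns continuity (yes/no): N = 55, odds ratio 3.2, 50% discordant pairs, two-sided 5%, at least 80% power. The discordant proportions are 0.5 × 3.2/4.2 = 0.381 and 0.5/4.2 = 0.119, a difference of 0.262. By the usual normal approximation, N = [(1.96 × √0.5 + 0.842 × √(0.5 − 0.262²)) / 0.262]² = 54.8, so 55, with power 0.80. The figure reproduces. It says nothing about Montevideo units or height, for which the plan gives no sizing figure and no expected mean or SD.

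**Assumed inputs.** For illustration: one value per woman and device, n = 55, IUPC mean 200 and SD 50. The mean, the SD and the scale factor k are assumptions; only n comes from the plan.

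**Case 1: perfect proportional tracking.** Let EUM = k × IUPC. The difference is (k − 1) × IUPC, with mean (k − 1) × 200 and SD |k − 1| × 50. Hence |t| = √n × mean/SD, and k cancels:

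- SD 50: √55 × 200/50 = 29.7
- SD 120: √55 × 200/120 = 12.4

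The test rejects decisively for every k other than 1, although the correlation is 1.

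**Case 2: near-perfect tracking.** Add independent noise with SD 5. At k = 0.95 the mean difference is −10 and its SD is √(2.5² + 5²) = 5.6, so |t| is about √55 × 10/5.6 = 13. A simulation of 4,000 replicates agrees:

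| k | Rejects | Mean correlation |
|---|---|---|
| 0.5 | 100% | 0.980 |
| 0.95 | 100% | 0.994 |
| 1.00 | 5.0% | 0.995 |
| 1.05 | 100% | 0.995 |
| 2.0 | 100% | 0.999 |

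**Case 3: equal means and SDs, varying correlation.** The SD of the differences is 50 × √(2(1 − r)), and the limits of agreement are ±1.96 times that:

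| r | Rejects | Limits of agreement |
|---|---|---|
| 0 | 4.9% | ±139 |
| 0.3 | 4.6% | ±116 |
| 0.9 | 4.9% | ±44 |

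The rejection rate stays near 5% throughout, so the test does not distinguish a device unrelated to the IUPC from one that follows it closely.

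**What n = 55 can deliver instead.** On a common scale, the 95% confidence interval for each limit of agreement has half-width t(0.975, n − 1) × √(1/n + 1.96²/(2(n − 1))) in units of the SD of the differences. At n = 55 this is 2.005 × √(0.0182 + 0.0356) = 0.46. At n = 110 (the 55 obese and 55 nonobese women together) it is 0.32. The plan gives no SD of the differences, so this cannot be turned into Montevideo units.

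**The case against.** The strongest reply is that the EUM channel may already be scaled to pressure. The Device Description says that it is the result of an algorithm, and the description of the notebook setup treats the fetal monitor's information as similar. A reader might infer that EUM and IUPC are on different scales and that unconverted values will be tested. The documents do not support this: they state neither a unit nor a transformation. The studies cited for EUM may contain a calibration, but that cannot be judged from the plan. If EUM does report calibrated Montevideo units, a scale error is true bias and the t-test is right to detect it. This part of the reply stands, and it limits the first gap to an unstated unit and derivation. It does not rescue the test as evidence of similarity, because Case 3 applies on any scale.

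A reader might also infer that totalling over a 30-minute tracing inflates the Montevideo figure. The plan does not define the window for the total, and multiplying both devices' simultaneous values by the same factor leaves the paired t statistic unchanged. All that is needed is a stated common window.

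Nor do the documents present contraction strength as the chief advantage of EUM over the tocodynamometer. The Introduction makes the claim about strength without that ranking.

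The general reference to nonparametric methods does not help either. A signed-rank test also examines the location of the differences and not their spread.

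Finally, these are two of fifteen secondary outcomes, and the plan says its results will inform more definitive studies. That is correct and bounds the importance of the point.

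**Conclusion.** The point holds for EUM v. IUPC Montevideo units and maximum contraction height. The plan declares the first comparable without giving a unit, a calibration or a derivation. It then compares both by a test that cannot show the similarity the Purpose section seeks. That the test responds only to the mean difference is a matter of algebra and needs no assumption. The sizes shown (|t| of 29.7 under perfect proportional tracking; about 5% rejection with limits of ±139 under no correlation) rest on the assumed mean of 200 and SD of 50. Whether the EUM scale actually differs from pressure is not known from the documents.

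The primary continuity outcomes and the stated sample sizes are unaffected. The change should be made before analysis, but it does not threaten the study's main comparison.

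**What to change.** 1. State the unit of the EUM uterine-activity output and how its Montevideo-unit equivalent is computed, with the same time window for both devices.
2. Do not use the paired t-test as the evidence of similarity for EUM v. IUPC Montevideo units and maximum height.
3. If the EUM output is on a calibrated pressure scale, report for both variables the mean bias and the 95% limits of agreement, each with a confidence interval.
4. If it is not, call the quantity an EUM activity index. Report its association with the IUPC for both variables, for example as the within-woman (repeated-measures) correlation across contractions or segments, with a confidence interval.

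The cost is a change of protocol and analysis wording. The recordings are the same and no sample size changes. The downside is that the study will report agreement or tracking for these two variables, and not a test of equal means.

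### Maximum contraction height is compared between EUM and tocodynamometer by paired t-test with no common scale, although the protocol says the tocodynamometer measures only frequency

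*Combined protocol and SAP*

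**What the plan says.** The Introduction limits what toco can deliver: "Although the tocodynamometer is noninvasive, it can only be used to measure contraction frequency". It describes a button pushed by the firming uterus, whose response "becomes more limited the greater the amount of adipose tissue interposed between it and the button".

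Objective 1 compares EUM, IUPC and toco tracings in obese and nonobese women on "the frequency of contractions, the duration of contractions, maximum height of the contractions, the total Montevideo units recorded", and then on timing and discontinuity. One restriction follows: "the Montevideo units will only be comparable between the IUPC tracings and the EUM device". Maximum height and duration are not restricted.

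Objective 3 concerns productive and non-productive contractions in triage. It uses toco and EUM only and again lists duration and maximum height.

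The Secondary Outcomes list in Materials and Methods includes "Compare maximum height of the contraction between the monitoring systems", with a parallel line for duration. Neither excludes toco. The Statistics section states: "A continuous outcome will be compared using a paired t-test".

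The protocol's background on the EUM describes its signal as uterine electrical activity. The Device Description lists separate uterine-activity columns for the EUM and for the clinical monitor and gives no unit or calibration for either.

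**The concern.** A paired t-test asks whether the mean of the within-woman differences is zero. That question has content only if both devices report the quantity on one scale. By the protocol's own account, toco height is not a measurement of contraction strength, and the documents give no conversion between it and the EUM signal.

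A significant result could then be reported as a difference between devices when it shows only a difference in scale. A non-significant one could be reported as agreement when the two scales merely happened to have similar means. The risk is greater here because the Purpose is to show the EUM superior to the external devices and the Objectives look at obese and nonobese women. If toco response falls with adiposity, the EUM-minus-toco height gap can widen in obese women even though the EUM performs identically in both groups. That could be misread as an EUM advantage specific to obesity.

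**Working it through.** **Passages side by side.**

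| Variable | Toco, per Introduction | EUM v. toco comparison, per Objective 1 and Secondary Outcomes | Common unit across EUM and toco? |
|---|---|---|---|
| Frequency | measurable | kept | yes (count per time) |
| Duration, timing | not measurable, if read literally | kept | yes (time) |
| Maximum height | not measurable | kept | none stated |
| Montevideo units | not measurable | excluded | not needed |

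Height is the one variable that both conflicts with the Introduction and lacks a common unit.

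**What an arbitrary scale does to the test.** The plan has no figure for this comparison to reproduce. The 55 women per group in the Statistics section come from a continuity calculation, not from height. The following is therefore an illustration on assumed data.

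Assumptions: 55 pairs; true height with mean 50 and SD 15 (arbitrary units); each device reads the same contractions with independent error of SD 5; toco readings are multiplied by a gain g.

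- Difference: d = EUM − g × toco
- Expected mean of d: 50 × (1 − g)
- Variance of d: 225 × (1 − g)² + 25 × (1 + g²)
- Test statistic: t = mean(d) / (SD(d) / √55)

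For g = 0.8 the expected mean is 50 × 0.2 = 10. The variance is 9 + 41 = 50, so the SD is 7.07 and the expected t is about 10 / (7.07 / 7.416) = 10.5. One simulated data set, with only g changed, gave:

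| Gain g | Expected mean difference | Simulated mean difference | t | p | Correlation |
|---|---|---|---|---|---|
| 0.6 | 20 | 20.0 | 17.5 | 7e-24 | 0.87 |
| 0.8 | 10 | 10.2 | 10.3 | 3e-14 | 0.87 |
| 1.0 | 0 | 0.4 | 0.43 | 0.67 | 0.87 |
| 1.2 | −10 | −9.4 | −8.8 | 5e-12 | 0.87 |
| 1.5 | −25 | −24.0 | −17.3 | 1e-23 | 0.87 |

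The contractions and the strength of association are the same in every row. The sign and significance of the t-test follow the gain alone.

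**BMI.** The Introduction implies a lower toco gain with more adipose tissue. If the gain were 1.0 in nonobese and 0.8 in obese women, the expected EUM-minus-toco differences would be 0 and 10. With 0.8 and 0.6 they would be 10 and 20. In both cases a gap of 10 units between BMI groups appears with no change in the EUM.

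**Alternative tests.** The Statistics section also allows non-parametric analysis in general terms. A signed-rank test works on the same differences and has the same defect.

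**The case against.** Five points can be made on the other side.

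1. **Duration.** A reader might infer that the EUM v. toco duration comparison is equally meaningless. The documents do not support that. Both devices give duration in time units, so a mean difference has a defined meaning and the scale argument does not apply. What remains is a wording conflict: the Introduction's sentence excludes toco duration, and Objective 1 includes it. The same sentence, read literally, would exclude timing too, so keeping timing while dropping duration would be inconsistent. The sentence is background and may simply be too broad.

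2. **Objective 3.** A reader might infer that it plans a direct test of EUM height against toco height. Its lead contrast is productive against non-productive contractions, which within one device needs no common scale. The mention of comparing the two devices' tracings leaves the other reading open, so the text is ambiguous and not plainly wrong.

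3. **Certainty of a false positive.** A reader might size the defect by the difference detectable with 80% power at 55 pairs, 0.385 SD of the paired difference. That holds for any paired t-test of this size and does not measure this defect. Nor is significance assured: the documents give no gain, and at a gain of 1.0 the illustration gives p = 0.67.

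4. **EUM v. IUPC.** The IUPC measures pressure and the EUM electrical activity, and no calibration is stated for that pair either. This stands as a caution. Restricting height to EUM v. IUPC relies on the comparability that Objective 1 asserts for Montevideo units, not on one that it demonstrates.

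5. **Stakes.** Height is one of many secondary outcomes. This stands and limits the weight of the point.

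None of these resolves the height conflict. No section withdraws toco from the height comparison or supplies a common scale.

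**Conclusion.** The point holds for maximum height in the EUM v. toco comparison of Objective 1 and the secondary outcomes. As planned, the mean paired difference would reflect scale and adiposity, could differ between BMI groups for that reason alone, and would not inform EUM accuracy. This rests on the Introduction's description of toco and on the absence of any stated unit, calibration or normalisation. If the recorded signals are in fact normalised to a common scale, stating so would change the conclusion. The numerical size is unknown; the table above shows how the result depends on an assumed gain.

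For duration and timing the defect is only an unreconciled contradiction, and for Objective 3 it is an ambiguity. The primary continuity outcomes, the frequency comparison and the sample sizes are unaffected. The change should be made, but the main results do not depend on it.

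**What to change.** - **Objective 1 and Secondary Outcomes:** add maximum height to the existing Montevideo-unit restriction, so that it is compared between EUM and IUPC only. If toco height is kept, state the units and normalisation of both signals and replace the paired t-test with a scale-free association measure, such as a within-woman rank correlation across contractions.
- **Objective 3:** state that height is contrasted between productive and non-productive contractions within a device, not between EUM and toco. That contrast is not a paired device comparison, so name a test for it.
- **Duration and timing:** reconcile the Introduction with Objectives 1 and 3 and the Secondary Outcomes. If the sponsor considers toco duration and timing readable, correct the Introduction's sentence and keep both comparisons. An agreement summary such as Bland-Altman limits would tell the reader more than a t-test alone.

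The cost is a few lines of text and, under the first option, the loss of one secondary comparison. No extra patients or data are needed.
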